1. SYNOPSIS

Study Title	Radiofrequency Power, Lesion Size Index and Oesophageal Temperature alerts during Atrial Fibrillation ablation: a pilot study	
Internal ref. no. / short title	PiLOT-AF study	
Study Design	Prospective, randomized, single centre observational clinical investigation	
Study Participants	Patients admitted for elective radiofrequency (RF) ablation for paroxysmal or persistent atrial fibrillation (AF)	
Planned Sample Size	80 patients (pilot study)	
Planned Follow-up duration	6 months	
Planned Study Period	15 months	
	Objectives	Outcome Measures
Primary	Assessment of the risk of oesophageal damage associated with radiofrequency (RF) ablation on the left atrial (LA) posterior wall when using different power settings	Luminal oesophageal temperature rises > 39°C during RF application on the LA posterior wall as recorded by an oesophageal temperature probe
Secondary	
Comparison of oesophageal complications with the different RF settings on LA posterior wall
 
Comparison of acute and short-term procedure success using different RF settings on LA posterior wall as marker of lesion transmural and durability
	
Symptoms of oesophageal injury during 6 months follow-up
 
Rate of first-pass pulmonary vein isolation (PVI), rate of acute pulmonary vein reconnection (PVR), total procedure time and RF time of the index ablation procedure
 
AF-free survival during 6 months follow-up

Tertiary	Comparison of rate of procedural complications using the different RF settings	pericardial effusion, TIA/stroke, phrenic nerve injury, pulmonary vein stenosis, open-heart surgery, death

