3.4 Research questions

On these premises, our research questions are:

- is it better to use higher RF powers for shorter times, than lower RF powers for longer times, to reduce the risk of oesophagus overheating and oesophageal temperature alerts?
- is the suggested LSI value of 5 on the LA posterior wall feasible or thwarted by frequent occurrence of temperature alerts leading to premature termination of RF delivery, regardless of maximum power?
- what is the impact of the different RF energy settings on PVI, acute pulmonary vein reconnection (PVR) and short-term clinical success of the AF procedure?
- which LSI value and RF power should be used during RF ablation on the LA posterior wall in order to achieve the best compromise between safety from oesophageal damage and lesion transmuralty and durability?

To these aims, the PiLOT-AF study aims to test different combinations of RF power and LSI during PV encirclement on LA posterior wall.

The rate of oesophageal alerts will be collected and compared for each procedure modality. The rate of first pass PVI and acute PVR (related to breakthrough signals on LA posterior wall), the procedure duration and RF ablation time will be also collected as clinical indicators of lesion transmuralty and acute procedure success. The freedom from AF at 6 months follow-up will be used as clinical indicators of lesion durability and short-term procedure success. The occurrence of any oesophageal symptoms at follow-up will be recorded as surrogate clinical indicators of oesophageal damage. All other procedural complications will be also recorded as safety outcomes.

No data are currently available on this topic. Therefore, this study has been designed as pilot study for power analysis and sample size calculation of a further main study.

This pilot study will hopefully give us some insights about the best combination of RF power, application time and target LSI to use during AF ablation on the LA posterior wall in order to achieve durable PVI with minimal risks of oesophageal damage.

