4. OBJECTIVES AND OUTCOME MEASURES

Objectives	Outcome Measures	Timepoint(s) of evaluation of this outcome measure (if applicable)

Primary Objective
 
To compare the risk of oesophageal damage associated with different RF settings during AF ablation on the LA posterior wall
	
Rate of oesophageal temperature alerts (defined as oesophageal temperature rise > 39°C) during RF ablation on the LA posterior wall
	
Index procedure

Secondary Objectives
 
1. To compare the acute success of the index AF ablation using different RF settings on the LA posterior wall
 
2. To compare the short-term success of the index AF ablation using different RF settings on the LA posterior wall
 
3. To compare the rate of oesophageal injury related to different RF settings on the LA posterior wall during the index AF ablation
	
1. Rate of first-pass PVI, rate of acute PVR related to breakthrough signals on the LA posterior wall, total procedure time and RF ablation time
 
2. Freedom from atrial fibrillation
 
3. Rate of oesophageal symptoms (difficult or painful swallowing, heartburn, acid reflux, sore throat, hoarseness, cough, nausea, vomiting, non-cardiac chest pain)
	
1. Index procedure
 
2. During the follow-up period (6 months)
 
3. During the follow-up period (6 months)

Tertiary objectives
 
To evaluate the rate of complications associated with the different RF settings
	
Pericardial effusion, TIA/stroke, phrenic nerve injury, pulmonary vein stenosis, open-heart surgery, death
	
Index procedure

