8.5. Arrhythmia Clinic visit at 3-4 months

As part of standard care, each patient will be reviewed in the Arrhythmia Clinic 3-4 months after the ablation to assess the current symptoms status and check the heart rhythm on ECG. In the case of recurrence of AF, the decision to restart an antiarrhythmic drug and/or to plan a redo procedure will be left to the clinician involved in the care of the patient. Moreover, in accordance with usual practice, additional investigations as prolonged ECG monitoring will also take place dictated by arrhythmia symptoms and assessment for potential adverse events related to the procedure.

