8.7. Discontinuation/Withdrawal of Participants from Study

Each participant has the right to withdraw from the study at any time. In addition, the Investigator may discontinue a participant from the study at any time if the Investigator considers it necessary for any reason including:

- Pregnancy
- Ineligibility (either arising during the study or retrospectively having been overlooked at screening)
- Significant protocol deviation
- Significant non-compliance with study requirements
- Withdrawal of Consent
- Loss to follow up

No specific procedures or observations will be required in case of discontinuation/withdrawal of participants from study rather than standard medical care.

The reason for withdrawal will be recorded in the CRF.

In case of withdrawal from the study in an early stage (before the intervention), the patient data will be excluded from the analysis and a new participant will be enrolled.

In case of withdrawal from the study during the follow-up period, neither exclusion of the data of that participant from analysis nor replacement with a new participant will be required.

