11.2. Description of Statistical Methods

Comparison of primary, secondary and tertiary outcome measures among different treatment groups will be performed at each time point using appropriate statistical testing. In particular, ANOVA tests will be used to compare numerical variables and chi-square tests will be used to compare categorical values.

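### AF-free survival has no time-to-event analysis: the plan lets a re-treated recurrence be scored as AF-free, and its named methods cannot censor withdrawals

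*Combined protocol and SAP*

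**What the plan says.** The outcome is worded in three ways:

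- Section 1 (Synopsis): "AF-free survival during 6 months follow-up".
- Section 4: "Freedom from atrial fibrillation", with the whole 6-month follow-up period entered as the time of evaluation.
- Section 3.4: "The freedom from AF at 6 months follow-up will be used as clinical indicators of lesion durability and short-term procedure success".

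Section 11.2 says that comparisons of all primary, secondary and tertiary outcomes "will be performed at each time point using appropriate statistical testing". It then names ANOVA for numerical variables and says that "chi-square tests will be used to compare categorical values". It mentions no survival method, event definition or censoring rule.

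After a recurrence, section 8.5 says that "the decision to restart an antiarrhythmic drug and/or to plan a redo procedure will be left to the clinician". Nothing says how such a patient is then scored.

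For withdrawal during follow-up, section 8.7 says that "neither exclusion of the data of that participant from analysis nor replacement with a new participant will be required". Section 11.3 adds that data already collected are analysed unless the patient asks otherwise. Neither section says what AF status such a patient has at 6 months.

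**The concern.** Section 3.4 makes this outcome the clinical indicator of lesion durability, and section 4 ties it to the index ablation. It should therefore record whether the randomised settings held without further help. If it is scored as status at 6 months, a success obtained by a drug or a redo is credited to the index settings. The failures that the outcome is meant to detect then disappear, and arms with different recurrence are pulled together.

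Withdrawal is a separate gap. The analysis keeps patients whose 6-month status is unknown, and neither named test can use partial follow-up. Someone must decide how to code them. Section 8.2.3 leaves the investigator unblinded to allocation, so that decision should be written down beforehand.

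**Working it through.** **The plan's own figures.** The documents give no expected AF-free rate, recurrence rate, re-treatment share or follow-up dropout, so there is no figure for this outcome to reproduce. The sample size rests on temperature alerts: 12 / 0.60 = 20 per arm, and 4 × 20 = 80. This matches section 11.1 at a 60% alert rate; the stated range of 75% to 55% gives 64 to 88. AF freedom does not enter, so nothing below changes the 80.

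**Which scoring rules fit the text?**

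- *Cumulative yes/no (any recurrence by 6 months).* This fits the word *during* in the synopsis and section 4, and the diary symptoms collected at the calls (section 8.6). A re-treated patient stays a failure.
- *Status at 6 months.* This fits the word *at* in section 3.4, the comparison by time point in section 11.2, and calls that assess current symptoms (sections 5 and 8.6). A re-treated patient can count as AF-free.

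The documents do not choose between them.

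**Re-treatment, under the status reading only.** Let r be the share recurring by 6 months and s the share of these who are AF-free again at 6 months. Both are assumptions. The 30-50% range for r borrows the repeat-ablation rate in section 3.1, which has no 6-month horizon. The 25-75% range for s has no source in the documents.

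- True freedom from first recurrence = 1 − r
- Status at 6 months = 1 − r(1 − s)
- Overstatement = r × s

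| r | s | True | Status | Overstatement (points) | Patients per 20 |
|---|---|---|---|---|---|
| 30% | 25% | 70% | 77.5% | 7.5 | 1.5 |
| 40% | 50% | 60% | 80% | 20 | 4 |
| 50% | 75% | 50% | 87.5% | 37.5 | 7.5 |

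The contrast between arms also shrinks. With s = 50% in both arms, true rates of 60% and 80% become 1 − 0.40 × 0.50 = 80% and 1 − 0.20 × 0.50 = 90%. The difference halves from 20 to 10 points. At 20 per arm and two-sided 5%, chi-square power falls from about 28% to 14%.

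**Withdrawal, under either yes/no reading.** Assume a constant recurrence hazard with r = 40%, and a share d withdrawing independently of recurrence and uniformly over 0-6 months. The chance that a withdrawer leaves before recurring is m = 0.40 / (−ln 0.60) = 0.783. With d = 10%:

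- Observed recurrences: 0.90 × 0.40 + 0.10 × (1 − 0.783) = 0.382. Counting the rest as AF-free gives 61.8%.
- Counting withdrawals without recurrence as failures: 0.90 × 0.60 = 54.0%.
- Leaving out only withdrawals without recurrence: 0.540 / (1 − 0.0783) = 58.6%.
- Leaving out every withdrawn patient: 0.540 / 0.90 = 60.0%, which is unbiased in this model.

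With d = 5-20% and r = 30-50%, the errors are +0.7 to +4.4 points (counted as free), −2.5 to −14 points (counted as failures) and −0.6 to −3.3 points (left out if without recurrence).

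**Power of the two tests.** For 60% against 80% AF-free, two-sided 5%, 20 per arm (12 events), chi-square has about 28% and log-rank about 30%. At 40 against 40, a pooling that the plan does not state, the figures are 50% and 53%.

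**The case against.** A reader might infer that the plan will score patients on their status at 6 months, so that re-treated patients will be counted as AF-free and withdrawn patients misclassified. The documents do not support that. Two of the three wordings are cumulative, and the time-of-evaluation entry in section 4 is the whole follow-up period. The diary gives information on the interval between contacts. Under that reading a re-treated patient remains a failure, and the re-treatment bias vanishes. Section 11.2 also allows for appropriate testing in general and does not tie chi-square to this outcome by name. All of this stands, and it limits the point to what the plan permits.

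Nor is misclassification of withdrawals established, because the plan gives them no classification. Section 11.3 keeps recurrences seen before withdrawal, and leaving out all withdrawn patients would be unbiased if withdrawal is independent of recurrence. With equal withdrawal in each arm, much of the error would cancel between arms. What remains is that a cumulative yes/no variable still needs a rule for these patients, whereas censoring supplies one.

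The upper end of the re-treatment range is doubtful. Patients are drug-refractory (section 7.2), a redo may only be planned at the 3-4 month visit, and follow-up ends at 6 months.

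The data are also coarse. After the procedure, Appendix B schedules an ECG only before discharge and at the 3-4 month clinic; prolonged monitoring depends on symptoms. The diary records symptoms and is not said to be dated. A survival curve therefore needs a definition of recurrence first. That is a fair demand on the fix, not a reason to leave the gap.

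**Conclusion.** The point holds as a gap in specification with a route to bias. The plan does not say whether AF freedom is cumulative or status at a visit, does not define recurrence, and has no scoring rule for re-treatment or for withdrawal before 6 months. The methods it names cannot censor.

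The possible size is large only for re-treatment under status scoring: 7.5 to 37.5 points, resting wholly on assumed recurrence of 30-50% and assumed return to freedom of 25-75%. Withdrawal shifts the estimate by under 5 points if such patients are counted as free or left out, and by up to 14 points if counted as failures at 20% withdrawal. These figures assume a constant hazard and independent, uniform withdrawal.

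The gain from a time-to-event analysis is a defined outcome and proper use of partial follow-up. Power rises by only about 2 to 5 points in the contrasts examined. This is a secondary outcome in a pilot of 20 per arm, so the change is worth making but does not threaten the study.

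**What to change.** In section 11.2, define AF-free survival as time from index ablation to first AF recurrence, and:

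- define recurrence from the ECG, clinic, diary and call data already collected, stating whether symptoms without a recorded rhythm count;
- count the first recurrence as the event, whatever drug or procedure follows;
- censor patients without recurrence at last contact;
- report Kaplan-Meier 6-month estimates with 95% confidence intervals by arm, and a log-rank test;
- state that dates are coarse because ECGs and contacts are few.

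Reword section 3.4 to agree with the synopsis and section 4.

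The cost is small but not nil: the CRF must record the date of first recurrence and of last contact, and the diary should ask for dates. No visits or patients are added, and clinical care under section 8.5 is unaffected.

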2. ABBREVIATIONS

ACT	Activated Clotting Time
AF	Atrial fibrillation
CF	Contact Force
CI	Chief Investigator
CRF	Case Report Form
CTRG	Clinical Trials & Research Governance, University of Oxford
GCP	Good Clinical Practice
FTI	Force Time Integral
GP	General Practitioner
ICF	Informed Consent Form
ICH	International Conference of Harmonisation
LA	Left atrium
LSI	Lesion Size Index
NHS	National Health Service
NRES	National Research Ethics Service
OXTREC	Oxford Tropical Research Ethics Committee
PI	Principal Investigator
PIL	Participant/ Patient Information Leaflet
PVs	Pulmonary Veins
PVI	Pulmonary Vein Isolation
PVR	Pulmonary Vein Reconnection
R&D	NHS Trust R&D Department
REC	Research Ethics Committee
RF	Radiofrequency
SOP	Standard Operating Procedure
TOE	Trans-Oesophageal Echocardiogram

3. BACKGROUND AND RATIONALE

3.1 Pulmonary Vein Isolation (PVI): rationale and pitfalls

Catheter ablation is a well-recognized treatment, with a class I indication, for symptomatic and drug-refractory atrial fibrillation (AF) (1-3). The current technique focuses on the elimination of mechanisms involved in the initiation and maintenance of AF. In this scenario, the pulmonary veins (PVs) are considered

to play a major role as the site of origin of ectopic atrial activity initiating and maintaining AF. Therefore, ablation of myocardium at the junction between the PVs and the left atrium (LA), leading to electrical isolation of the PVs, is currently the cornerstone of the treatment of both paroxysmal and persistent AF (4, 5). Unfortunately, although pulmonary vein isolation (PVI) can be achieved acutely in up to 100% of cases, recovery of electrical conduction of one or more arrhythmogenic PVs is quite common, both acutely and chronically. Acute pulmonary vein reconnection (PVR) is observed before the end of the ablation procedure in up to 50% of cases (6). Even if PVI is reached and maintained until the end of the procedure, chronic PVR is found in up to 80% of redo procedures performed for arrhythmia recurrence (7). As a consequence of reconnection rate, AF or associated atypical flutter recurrences lead to repeat AF ablation procedures in 30-50% of patients (8).

Although the pathological basis of PV reconnection is not yet known, it is suspected to result from deficiencies of the index ablation procedure, specifically gaps in the initial line of ablation, and/or failure of initial lesions to deliver permanent, transmural necrosis and permanent scar. Of note, recent histological data have correlated partial thickness ablation lesions with chronic and persistent PV conduction (9).

3.2 Radiofrequency (RF) ablation: principles and determinants of lesion formation

For radiofrequency (RF) energy delivered through an irrigated-tip ablation catheter, the reasons for lesion failure are multifactorial.

RF energy generates an ablation lesion through tissue heating. The transformation of electromagnetic energy into thermal energy, as electrical current passes through a resistive medium, is responsible for direct resistive heating in the narrow rim of tissue in close contact with the catheter electrode (2 to 3 mm). However, because direct resistive heating of the tissue decreases proportionally with the distance from the electrode to the fourth power, heating of deeper tissue layers occurs passively through heat conduction. While resistive heating is a fast process, taking place in a few seconds, conductive heating is a much slower process, requiring up to 30 sec (10, 11). In this process, delivered power, application time and catheter tip-tissue contact pressure all play a role (12, 13). Higher power delivery increases the source temperature and the radius of the heat source (although it hardly exceeds 2-3 mm regardless of the delivered power), thereby increasing lesion size in two ways. Time is required for thermal conduction to deeper tissue layers. Greater electrode-tissue contact pressure increases lesion size by improving electrical coupling with the tissue, increasing the electrode surface area in contact with the tissue, and reducing the shunting of current to the blood pool.

It has been demonstrated that the maximum lesion size is achieved after 40 to 60 seconds of RF delivery and longer RF deliveries increase the risk of complications without a substantial benefit in terms of lesion formation (36).

Contact force (CF)-sensing ablation catheters, able to monitor constant, real-time contact force during mapping and ablation, are now available for clinical use (14-16). Moreover, formulas combining contact force, RF power and application time such as Force Time Integral (FTI) (17) or Lesion Size Index (LSI) have been developed in order to predict the lesion size and depth and to guide the RF ablation. In particular, LSI is a non-linear function that combines power, CF and ablation duration; it has been found to be especially effective in calculating gap formation and estimating lesion quality (18).

Based on clinical studies (19-24), the current CF recommendations to achieve transmural lesions and durable PVI are: minimum CF > 10 g with target CF of 20 g, target FTI > 400 gs, suggested LSI \geq 6 on the LA anterior wall, \geq 5 on the LA posterior wall and \geq 5.5 on the LA roof and floor.

Among the different parameters (RF power, CF, FTI, LSI), LSI seems to be the best predictor of lesion size and gap formation at 3 months post-PVI (23).

3.3 Oesophageal damage and atrio-oesophageal fistula after AF ablation

Unfortunately, deeper lesions mean a higher risk of overheating and damage of extra-cardiac structures close to the LA, in particular the oesophagus when ablating on the LA posterior wall. Heating of the connective tissue layer between the LA and oesophagus, containing oesophageal vascular structures, and of the oesophageal wall itself, are thought to contribute to the genesis of atrio-oesophageal fistulae, a rare but fatal complication of AF ablation (25).

In view of the variable position of the oesophagus relative to LA posterior wall, its positional changes over time and of the variable thickness of the posterior LA wall, fat pad and connective tissue layer between the LA and oesophagus, the prevention of oesophageal damage during AF ablation is quite challenging (26-29).

Lower RF powers and shorter application times are usually used on the LA posterior wall but this is a completely empirical approach which has not been proved to be effective in preventing oesophageal damage. Continuous luminal oesophageal temperature monitoring during the AF procedure is a suggested strategy to prevent oesophageal damage related to AF ablation. The rationale behind this strategy is that luminal oesophageal temperature is a surrogate marker of the mural temperature and therefore it can predict and avoid tissue damage. Observational studies employing real-time luminal oesophageal temperature measurements during LA catheter ablation have shown that lower oesophageal luminal temperatures are associated with lower rates of oesophageal ulcerations detected by endoscopy after ablation (30-33). To this aim, a temperature probe is inserted nasally or orally and advanced to the level of the posterior LA under fluoroscopic guidance where it permits real-time intraluminal oesophageal temperature monitoring during the ablation. Moreover, it marks the location of the oesophageal lumen that can also be visualized in the electro-anatomical map to evaluate the distance of the ablation catheter tip from it. Different oesophageal temperature probes are currently available: single-sensor ones, linear multi-sensor and 2-dimensional sinusoidal multi-sensor ones. The advantage of the multi-sensor probes, and especially of the sinusoidal one, is that their design allows for a greater area of temperature monitoring and their position does not require adjustments to be in close vicinity of the ablation catheter tip during RF delivery (34).

When using an oesophageal temperature probe-guided ablation strategy, RF delivery on the LA posterior wall is promptly terminated in case of any oesophageal temperature rises $>39^{\circ}\text{C}$ and power is reduced in contiguous sites. However, the big challenge of this approach is in not knowing how much delivered RF energy is both simultaneously “safe” and “effective”.

In our experience, oesophageal temperature alerts are very common during PV encirclement on LA posterior wall, occurring in the majority of procedures and, regardless of the power used, they tend to occur before the achievement of the suggested LSI of 5. Moreover, lower RF powers are generally used on LA posterior wall but, in view of the strict relation between power and application time in determination of

lesion size, the adoption of lower RF powers usually implies longer RF applications in order to reach the suggested LSI and maximize the chance to achieve a durable PVI.

Interestingly, the relationship between RF energy settings and oesophageal temperature alerts is anything but clearly defined (35). Of note, the oesophageal injury during LA ablation is attributed to conductive heat transfer from the ablation site, a time-dependant process.

